## 10.0 DATA MANAGEMENT/CONFIDENTIALITY

The investigator will ensure that data collected conform to all established guidelines. Each subject is assigned a unique subject number to protect subject confidentiality. Subjects will not be referred to by this number, by name, or by any other individual identifier in any publication or external presentation. Subject research files are stored in a secure place (or database). Access is restricted to authorized personnel.

### 10.1 Source Data to be Recorded Directly

There are 6 sources of data for the study: (1) screening survey (2) baseline survey, (3) contact form, (4) 3-month follow-up survey, (5) 6-month follow-up survey, and (6) 12-month follow-up survey. We will also collect automated utilization data from the QuitBot CA program, Google Analytics, and SmokefreeTXT program. All data will be collected directly from consenting adult participants. A description of these sources of data follows.

**Survey Data.** The Baseline Survey, hosted on our secured recruitment website, will collect data on (1) demographics, (2) nicotine and tobacco use, (3) nicotine dependence, (4) readiness to quit, (5) quit attempts, (6) smoking costs, (7) quality of life, (8) interpersonal trust, (9) social support, and (10) contact information needed for the study's follow-up data collection activities – as well as information about whether or not it is acceptable to receive email or voice messages and mail from

the study. The 3-month survey will primarily collect data on intervention processes (e.g., therapeutic alliance), cessation progress (e.g., quit attempts) and outcomes (e.g., 30-day abstinence), and the participant's experiences with their assigned smoking cessation intervention. The 6- and 12-month surveys will primarily collect data on cessation progress/outcomes.

**QuitBot CA utilization data and security.** The QuitBot CA program will be accessible to participants when they access the download and login link sent to them in their secure trial enrollment email. During the enrollment process, participants check their smartphone storage requirements and opt-in to download the app. If the participant is then randomized to the QuitBot arm, a randomly-generated opt-in ID is sent to the QuitBot backend, where it is whitelisted and connected to their user data, which allows them to fully interact with the bot content. Non-whitelisted users who attempt to download the app will not be able to login and will receive a single generic response, redirecting them to the study website page for more information. The CA will collect information on participants' responses to the program, including triggers to smoke (physical, emotional, and situational triggers), motivations to quit, barriers to quitting, and number of cigarettes smoked in end-to-end encrypted "private conversations", and it will not collect PHI. Data will also be collected on usage information: the number of days user interacted with assigned intervention and whether users completed assigned intervention. This information will be extracted over a secure connection on a weekly basis, and stored on a secure internal Fred Hutch server. A raw copy of the data serves as an additional backup beyond the ongoing built-in Azure storage backup processes. An automated script creates a fully de-identified and cleaned copy of the data, to send to the study team analysts. This usage data can be tied to the survey data using the aforementioned randomly generated opt-in IDs.

**SmokefreeTXT utilization data and security.** Participants randomized to the SmokefreeTXT arm will be asked to provide a quit date on a website with data transmission via Transport Layer Security (TLS.) A schedule of text messages is set up based on the quit date. Participants can request that messages be stopped at any time. Date stamps and content of the outgoing messages and incoming messages with participant responses to queries about mood, cravings, relapse, and smoking status will be stored on secured Fred Hutch servers. These data will only be accessible to Fred Hutch Shared Resource programmers and not accessible via websites. The programmers will prepare de-identified utilization data for analysis.

**Remote biochemical verification data and security.** After completing each survey, 10% of all participants randomly selected at randomization to complete the biochemical verification procedure will be mailed a Alere saliva-based smoking cessation verification test and instructions. Participants will take the test, and upload photos of themselves taking it and their test results in a secure online survey. Anyone having difficulty with the online version of the test can contact study staff, who will help participants conduct the test and display their results using Doxy.me, an encrypted live video-conferencing software available at Fred Hutch. The Doxy.me software is accessible via smartphone, tablet, or desktop computer, does not require participants to set up accounts or do downloads, plugins, or installations because it works in all popular web browsers. It uses 128-bit encryption, does not record PHI or store data, and is compliant with HIPAA and HITECH requirements. The online survey version of the biochemical verification has the same security features as our other online surveys: information will be extracted over a secure connection and stored on a secure internal Fred Hutch server, identified by alphanumeric IDs only. Fred Hutch Shared Resource programmers will be the only persons with the ability to re-identify study participants based on the alphanumeric IDs. The programmers will prepare de-identified utilization data for analysis.

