## **2.4 Risks/Benefits**

### **2.4.1 Potential Risks.**

The main risk to participation in this study is breach of confidentiality.

A breach of confidentiality could possibly occur if, for example, an unauthorized person accesses the study's database records, QuitBot app records, text message log, and/or study hard copy records, or if telephone survey conversations are accidentally overheard by someone who does not know the participant smokes or is taking part in a smoking cessation study. Also, some participants might feel emotional upset during their assigned intervention or embarrassment when talking about their smoking during the telephone surveys. Finally, some smokers making quit attempts may experience some short-term discomfort associated with nicotine withdrawal.

Participants will be fully apprised of all anticipated risks in the informed consent and other intervention materials, and will have the option to opt out of the trial at any time.

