## 8.0 ADVERSE EVENTS

### 8.1 Adverse Event

According to ICH guidelines (Federal Register. 1997; 62(90):25691-25709) and 21 CFR 312.32, IND Safety Reports, and ICH E2A, Definitions and Standards for Expedited Reporting, an adverse event is defined as follows:

An adverse event is any untoward medical occurrence in a clinical investigation subject administered a medicinal product and which does not necessarily have a causal relationship with this treatment. An AE can therefore be any unfavorable and unintended sign (including an abnormal laboratory finding), symptom, or disease temporally associated with the use of a medicinal product, whether or not considered related to the medicinal product.

Abnormal laboratory values for laboratory parameters specified in the study should not be recorded as an adverse event unless an intervention is required (repeat testing to confirm the abnormality is not considered intervention), the laboratory abnormality results in a serious adverse event or the adverse event results in study termination or interruption/discontinuation of study treatment.

Medical conditions present at screening (i.e., before the study treatment is administered) are not adverse events and should not be recorded on adverse event pages of the CRFs. These medical conditions should be adequately documented on the subject chart. However, medical conditions present at baseline that worsen in intensity or frequency during the treatment or post-treatment periods should be reported and recorded as adverse events.

For this trial, an example of an unexpected event that is not adverse is a participant who has become very unhappy with trial procedures. Adverse events (AEs) are any untoward occurrence with a trial participant whether or not it can be considered to be related to their smoking cessation intervention (the QuitBot CA or SmokefreeTXT programs). An example of an adverse event in this trial could include an increase in depressive symptoms. Serious adverse events (SAEs) include any AE that results in death, a real risk of dying, inpatient hospitalization, persistent or significant disability/incapacity, or AEs that require intervention to prevent permanent impairment or damage. In this trial, an example of a serious adverse event would be a suicide attempt.

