### 8.5 Adverse Event Recording Period

Throughout the study, the Principal Investigator, Co-Investigators, and Project Manager will monitor participants for adverse events and protocol compliance. The Project Manager will complete monthly reports on participant progress and status, any adverse events, and any protocol deviations. Protocol adherence will be monitored by the PI.

Study staff will be trained, and required, to report all unexpected and adverse events to the PI during the study recruitment, intervention, and follow up periods. Adverse events beyond what would be expected in the course of smoking cessation will be reported to the Fred Hutch's IRB in accordance with Fred Hutch policy.

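### The protocol commits to monitoring adverse events, but no described data source asks participants about them, and the detection routes it does describe differ by arm

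*Combined protocol and SAP*

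**What the plan says.** Section 8.5 says of the investigator, co-investigators and project manager that they "will monitor participants for adverse events and protocol compliance", and this is to run throughout the study. Section 8.1 treats a condition that worsens from baseline as an adverse event and adds: "An example of an adverse event in this trial could include an increase in depressive symptoms". Section 8.3 requires every adverse event to be assessed and entered on case report forms with onset and resolution dates, severity, relatedness, action taken and outcome. Section 9.0 has adverse events and safety reviewed twice a year by the investigators, and adverse events reviewed at least annually by oversight committees. Section 2.4.1 names the expected risks, including emotional upset, and notes that "some smokers making quit attempts may experience some short-term discomfort associated with nicotine withdrawal".

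Section 10.1 opens its account of data collection with "There are 6 sources of data for the study": screening survey, baseline survey, contact form, and the 3-, 6- and 12-month surveys. It adds: "We will also collect automated utilization data from the QuitBot CA program, Google Analytics, and SmokefreeTXT program". The baseline survey has ten listed topics, among them "7) quality of life, (8) interpersonal trust, (9) social support". The 3-month survey mainly covers intervention processes, cessation and "the participant's experiences with their assigned smoking cessation intervention". The two later surveys mainly cover cessation.

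**The concern.** The safety sections describe what happens once staff know of an event: classification (8.4), internal reporting (8.5) and onward reporting (8.6). They do not say how staff come to know of it. In a remote trial with no visits, that step has to be designed. If nobody asks, the count depends on who volunteers information and on which automated checks run in each arm. A low count then cannot separate few events from few reports, and a difference between arms cannot separate harm from detection. The uses at stake are the section 9.0 reviews and any later reporting of adverse events by arm.

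**Working it through.** The check sets the safety commitments beside every collection route in the document. No rate or power calculation applies.

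**Sources listed in section 10.1**

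| Source | Described as asking about adverse events or depressive symptoms? |
|---|---|
| Screening survey | No |
| Baseline survey | No; the nearest topic is quality of life |
| Contact form | No |
| 3-month survey | No; the nearest topic is experience with the intervention |
| 6-month survey | No |
| 12-month survey | No; section 11.3 adds EQ-5D, used for the cost-per-QALY analysis |

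Count: 0 of 6. The case report forms required by section 8.3 are not listed either.

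**Utilization feeds (three are named)**

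- QuitBot: use of the program and smoking-related content, including emotional triggers to smoke. A trigger is a cue for smoking, not a measure of depressive symptoms.
- Google Analytics: no safety content is described.
- SmokefreeTXT: stores replies to queries about mood. Access is limited to programmers, who prepare de-identified data for analysis. No safety review is described.

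Count: 1 of 3 feeds is described as holding replies to mood queries, in one arm only.

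**Other routes**

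| Route | Section | QuitBot | SmokefreeTXT |
|---|---|---|---|
| Suicide and self-harm keyword alert to staff | 2.4.2 | Described | Not described |
| Participant may email the investigator | 2.4.2 | Yes | Yes |
| Staff must report events they learn of; monthly project report | 8.5 | Yes | Yes |

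The last two rows apply equally to both arms but are passive. The only automated safety alert is described in 1 of 2 arms.

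**Reach of the telephone survey as a staff contact.** Section 7.2 plans for an 85% response, with about 92% of completers online. The share completing by phone or mail is 0.85 × (1 − 0.92) = 0.068. Applied to 1,647 participants, 0.068 × 1,647 ≈ 112. On the plan's own expectations, then, roughly 112 people per survey would respond other than online, and fewer by phone. Some others may speak to a caller and then finish online or not at all, so this is only a guide. It does show that mentioning a problem to a surveyor is not a general detection route.

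**Depressive symptoms in particular.** To show an increase, a baseline value and a later value are needed, or a direct question about change. Section 10.1 describes neither.

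**The case against.** Several counter-arguments have force.

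- *The list is not closed.* The surveys *primarily* collect the named topics, the questionnaires are not in the documents, and biochemical verification is described in section 10.1 without being one of the six sources. An unlisted safety item is possible. This stands, and it limits the point to what is described. Even so, a source on which section 8 depends should be named.
- *Some mood data exist.* A reader might infer that no source collects mood. The SmokefreeTXT replies contradict that. What is missing is a described safety use of those replies and an equivalent in the other arm.
- *Detection is not left to chance.* A reader might infer that events surface only by accident. The keyword alert, the email route and mandatory staff reporting rule that out. But the alert is narrow and described for one arm, and the other two depend on someone volunteering the information.
- *No adverse event comparison is planned.* Section 11 contains no safety endpoint or test, so the gap invalidates no planned analysis. This stands. The consequence is for the section 9.0 reviews and for any by-arm reporting.
- *The trial is classed as minimal risk, and the depressive-symptom sentence is illustrative.* Both are true. They reduce the urgency but do not remove the commitment to monitor throughout.

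**Conclusion.** The point holds in a limited form. As described, adverse event capture is passive, and its automated element differs by arm: 0 of 6 listed sources are described as soliciting events or depressive symptoms, the keyword alert is described for QuitBot only, and stored mood replies for SmokefreeTXT only. Counts may be incomplete, and a difference between arms could reflect ascertainment.

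The direction and size of any bias cannot be derived. It is tempting to conclude that the trial would record almost no events, but the documents give neither an event rate nor a capture fraction, so that conclusion is unsupported. The finding assumes that the description in section 10.1 is substantially complete and that no matching alert runs in the SmokefreeTXT arm. If the questionnaires already hold a common safety item, the remedy reduces to naming it. The primary cessation analysis is unaffected. This is an improvement worth making at low cost.

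**What to change.** 1. Add one short fixed question to the follow-up surveys still to be sent, with the same wording and timing in both arms and collected by the blinded survey unit. It should ask about any hospitalization and any new or worsened mood or health problem, with onset date. The recall period is since enrolment at the first survey that carries the question, and since the last survey thereafter.
2. Route positive answers into the existing section 8 process, and name this source and the adverse event case report form in section 10.1.
3. Report solicited events by arm, separately from spontaneous and keyword-alert events.
4. For participants already past their final survey, state that capture was passive and that between-arm adverse event counts are not interpretable.

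The cost is an amendment, slightly longer surveys, and more events to classify and report. The gain has limits. Section 3.4 records all 1,647 participants as accrued, so no baseline mood measure can be added. Recall over months will also not fully capture events near the quit date.

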#### 3.3.1 Primary Endpoint

The primary endpoint is 30-day biochemically confirmed cigarette smoking cessation at 12 months after randomization.

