### 11.2 Primary/Secondary Endpoints/Hypotheses and Analytical Methods

[figure not shown]
The primary endpoint will be biochemically-verified 30-day point prevalence at 12 months post randomization. Secondary endpoints will be 30-day biochemically confirmed point-prevalence at 3 and 6 months post randomization. Consistent with remote digital cessation study methods [1, 18], biochemical confirmation will be conducted on participants self-reporting no smoking at all in the last 30 days.

Our primary outcome hypothesis is that QuitBot will have significantly higher 30-day point prevalence abstinence at 12 months post-randomization than SmokefreeTXT. For each comparison of the treatment arms on the primary and all secondary endpoints, we will use a logistic regression model. Using standard smoking cessation trial intent-to-treat analysis, all missing outcomes will be coded as smokers [31, 35-39]. The model will adjust for all stratification factors as well as baseline factors that are imbalanced after randomization and significantly related to the outcome. In addition, we will conduct these sensitivity analyses: (1) multiple imputation of missing outcomes [107-109], (2) complete case analysis of those providing follow-up data, (3) using a secondary cessation outcome of no use of cigarettes and other nicotine or tobacco products except FDA-approved nicotine replacement therapies, (4) adjusting for baseline usage of other tobacco and nicotine products, and (5) adjust for usage of other interventions and cessation medications after study enrollment.

[figure not shown]

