11.5 Sample Size and Power

We determined sample size for binomial proportions aimed at 80% power for Primary Objective 1 using the following parameters: (1) randomized to one of the two interventions; (2) conservative 12-month outcome survey response rate of 85%, based on our most recently published large RCT comparing two digital interventions [84]; (3) 80% completion rate of biochemical verification [103, 104]; (4) intent-to-treat analysis where, as standard in digital intervention smoking cessation trials, all those with missing data (including missing biochemical data) are coded as smokers [1, 121]; and (5) two-sided test with  $\alpha = .05$ . We adjusted all power analyses for expected non-response rates and biochemically-confirmed cessation rates so that outcomes would not be inflated.

Power for Objective 1: Objective 1 will compare 12-month quit rates between QuitBot vs. SFT. Projected quit rates at 12-month follow-up were conservatively calculated using (1) quit rates at 3-month follow-up in our pilot RCT, along with (2) well-established relapse curves, which provide a data-derived estimate (i.e., 20-35%) of the rate of decay of intervention effects by 12-month follow-up [90, 91, 122]. We estimated a relapse of 27% (between 3 and 12 month-follow-up) and survey response and biochemical verification completion rates of 85% and 80%, respectively. The 12-month quit rate for SFT is conservatively estimated as 9.3%, as consistent with the projected SFT 12-month relapse rates from the pilot RCT and the 8.4% average quit rate from the most recent meta-analyses [1, 2, 18-21]. As shown in Table 5, obtaining 80% power to significantly detect a quit rate as low as 13.9% for QuitBot (vs. 9.3% for SFT) requires 1,520 randomized participants, with 760 in each study arm.

Table 3. Objective 1 Sample Size Estimates.

	Projected relapse rate				
	20%	25%	27%	30%	35%
	QuitBot 12-month follow-up 30-day point prevalence quit rate				
	15.2%	14.3%	13.9%	13.3%	12.4%
Total in each arm	484	653	760	983	1,579
Total randomized	968	1,306	1,520	1,966	3,158

This very conservatively estimated 13.9% quit rate would have high public health impact—49% higher impact than the projected 9.3% quit rate for SFT and 65% higher than the average 8.4% quit rate observed in text messaging interventions [1, 2, 18-21].

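### The plan sends the saliva test to a random 10% of participants, defines a biochemically verified primary endpoint, and does not say how the other 90% are classified

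*Combined protocol and SAP*

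**What the plan says.** Four parts of the combined protocol and SAP bear on who is tested and who counts as a quitter.

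- **Section 10.1** (remote biochemical verification) states, for every follow-up once the questionnaire is in: "10% of all participants randomly selected at randomization to complete the biochemical verification procedure will be mailed a Alere saliva-based smoking cessation verification test". Selection is fixed at randomization, before any smoking status is reported.
- **Sections 3.3.1 and 11.2**: "The primary endpoint is 30-day biochemically confirmed cigarette smoking cessation at 12 months after randomization", and again "The primary endpoint will be biochemically-verified 30-day point prevalence at 12 months post randomization". Sections 3.3.2 and 11.2 define the 3- and 6-month secondary endpoints the same way.
- **Section 11.2**: "biochemical confirmation will be conducted on participants self-reporting no smoking at all in the last 30 days", with no mention of a sample. For the analysis, "all missing outcomes will be coded as smokers".
- **Section 11.5**: the sample size assumes an 85% survey response and an "80% completion rate of biochemical verification". It also states that "all those with missing data (including missing biochemical data) are coded as smokers". The section says its quit rates already allow for both losses.

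No section says how a participant outside the 10% sample is classified in the primary analysis.

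**The concern.** A verified endpoint needs a test result, or a rule for its absence, for everyone who reports abstinence. Section 10.1 provides a test for about one participant in ten. Section 11.5 is built as if the test goes to essentially every self-reported abstainer and four in five complete it. The two sections describe different procedures.

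What is at stake is the definition of a quitter. Depending on how the gap is filled, the same participants give confirmed rates near 1%, the planned rates near 9% and 14%, or self-reported rates that are higher still. Enrolment is already complete (Section 11.1), and Section 9.0 has the investigators reviewing interim outcome data. An open choice could therefore be settled after results are known. The serial mediation model and the life-year calculation in Section 11.3 use the primary outcome or endpoint by name and inherit the problem. Cost per quitter (Section 11.3) and the moderator models (Section 11.4) refer only to 30-day abstinence, so it is unclear which definition they use.

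**Working it through.** **Inputs.** From Section 11.5: projected 12-month rates 9.3% (SFT) and 13.9% (QuitBot), two-sided alpha 0.05, 80% power, 760 per arm, 85% survey response, 80% verification completion. From Section 10.1: a 10% sample. From the synopsis and Section 3.1.1: 823 per arm.

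**Step 1: reproduce the plan's sample size.** With pooled variance under the null and mean rate p̄ = 0.116:

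n = [1.96·√(2·0.116·0.884) + 0.8416·√(0.139·0.861 + 0.093·0.907)]² / 0.046² = (0.8876 + 0.3802)² / 0.002116 ≈ 759.6, so 760 per arm.

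This matches the plan, and the other four columns of its Table 3 also reproduce exactly. The corresponding power is 80.0% at 760 and 83.1% at 823 per arm. The sample size arithmetic is not in error.

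**Step 2: unselected participants count as missing, hence smoking.** Only the 10% sample can supply a confirmed quitter.

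- Ceiling if every participant quit: 10%. After the plan's completion rates: 0.10 × 0.85 × 0.80 = 6.8%. The projected 13.9% is above both limits; the projected 9.3% is above the second.
- Expected rates: 0.10 × 9.3% = 0.93% and 0.10 × 13.9% = 1.39%.
- Expected confirmed quitters at 823 per arm: 823 × 0.0093 = 7.7 and 823 × 0.0139 = 11.4.
- Power = Φ{[0.0046·√823 − 1.96·√(2·0.0116·0.9884)] / √(0.0139·0.9861 + 0.0093·0.9907)} = Φ{(0.1320 − 0.2968)/0.1514} = Φ(−1.089) = 13.8%. At 760 per arm it is 13.1%.
- 80% power at these rates would need 8,505 per arm. Even with every sampled abstainer completing the test (1.16% versus 1.74%), power is 16.2% at 823.

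**Step 3: unselected participants count on self-report.** The plan gives no self-reported rates. Assume they equal the stated rates divided by 0.80, with no test refuting a report.

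- 9.3%/0.80 = 11.6% and 13.9%/0.80 = 17.4%.
- Power is 91.3% at 823 and 89.0% at 760.
- Range: with a divisor of 1 (self-reported rates no higher than the stated ones), power at 823 is the 83.1% of Step 1. Over divisors from 1 to 0.80 it runs from about 83% to 91%.
- Hybrid, with missing tests in the 10% sample still coded as smoking: 0.9 × 11.625% + 0.1 × 9.3% = 11.4%, and 0.9 × 17.375% + 0.1 × 13.9% = 17.0%; power 90.6% at 823.

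**Step 4: what the 10% sample can show about misreporting.** Under the Step 3 assumption, the sampled 82.3 per arm contain 82.3 × 0.116 = 9.6 and 82.3 × 0.174 = 14.3 self-reported abstainers. At 80% completion, 7.7 and 11.4 return a test. As an illustration only, 2 discordant results out of 11 has an exact 95% interval of 2% to 52%.

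| Treatment of the unselected 90% | SFT v QuitBot | Power, 760/arm | Power, 823/arm |
|---|---|---|---|
| None unselected: all abstainers tested | 9.3% v 13.9% | 80.0% | 83.1% |
| Missing, coded as smoking | 0.93% v 1.39% | 13.1% | 13.8% |
| Counted on self-report (divisor 0.80) | 11.6% v 17.4% | 89.0% | 91.3% |

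**The case against.** The strongest reply is that no sensible analyst would code nine tenths of the trial as smokers because they were never sent a kit. Not being sampled by design is not obviously the same as missing. The explicit reference to missing biochemical data stands in the sample size section, while the analysis section speaks only of missing outcomes. Section 10.1 is a paragraph on data sources and security, not the endpoint definition, and the 10% may be only a validation sample. Section 11.2 does not say that every abstainer is tested; it could mean abstainers within the sample. It also plans multiple imputation and complete-case sensitivity analyses.

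Much of this stands. A reader might infer that the primary analysis as written must collapse to 14% power. The documents do not support that, because it requires unselected participants to count as missing, which no section states. Nor are the rules logically incompatible: Step 2 applies them together. What fails under that reading is the pair of projected rates. A reader might also infer that every downstream analysis loses its outcome, but cost per quitter and moderation are not tied in words to verification.

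The reply does not remove the problem. If the 10% is only a validation check, no section says so, and the endpoint label, the rule on missing biochemical data and the 0.80 factor are then wrong. If Section 11.2 means all abstainers, Section 10.1 is wrong. If it means abstainers within the sample, the rest remain unclassified. Sensitivity analyses do not define the primary one.

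The self-report figures are also softer than the others. The stated rates do not follow from the pilot rates and the listed factors: 32% × 0.73 × 0.85 × 0.80 = 15.9%, and 23% × 0.73 × 0.85 × 0.80 = 11.4%. Dividing by 0.80 is therefore an assumption about how the stated rates were built.

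**Conclusion.** The point holds as an internal inconsistency that must be resolved: on each reading, at least one stated rule or figure needs correcting. The size depends on the reading. Like for like at 823 per arm, power is 13.8% if the unselected count as missing and 83.1% if all self-reported abstainers are tested. On self-report it is about 91%, but for an endpoint other than the stated one. The first two figures use only the plan's own numbers plus the named reading; the third needs the 0.80 assumption. The low figure describes one reading and is not a prediction for the trial. The contradiction itself depends on none of these calculations.

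**What to change.** Before outcome data are examined, state who is tested and how participants outside the sample are coded, and make Sections 10.1, 11.2 and 11.5 agree.

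- **If only the 10% sample is tested:** define the primary and secondary endpoints as self-reported 30-day point prevalence, here and in the synopsis and Sections 3.1.1, 3.3.1 and 3.3.2. Remove missing biochemical data from the missing-equals-smoking rule. Restate the rates and power without the 0.80 factor. Report the sample by arm, with confidence intervals, as an imprecise check on misreporting. This needs no new data but gives up the verified label.
- **If all self-reported abstainers are tested:** correct Section 10.1 to say so and keep Section 11.5. Under the Step 3 assumption this needs 823 × (0.11625 + 0.17375) ≈ 240 kits at 12 months, plus kits at 3 and 6 months. Section 10.1 as written already mails kits to smokers and abstainers alike in the sample: 0.10 × 1,647 ≈ 165, or about 140 at 85% response. If the new kits replace those, the net addition at 12 months is about 100.

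In either case, state which outcome definition the cost-per-quitter and moderator analyses use. Apart from the kits, the cost is wording and, under the first option, a restated power figure.
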